**7.4. Standard Analyses**

**7.4.1. Disposition of Subjects**

Subject disposition, including the number of subjects enrolled, number of subjects treated, number of subjects evaluated for safety and number of subjects who completed the study or withdrew early (including reasons for withdrawal) will be summarized by treatment group for the ITT population.

Disposition information will be listed.

---

|           |   |                 |           |
|-----------|---|-----------------|-----------|
| Document: | C:\Users\q764206\AppData\Local\Microsoft\Windows\Temporary Internet Files\Content.Outlook\GWW33WM3\ATLAS_SAPFinal v8.0_06MAR2018.docx |                 |           |
| Author:   | [name] (Updated [name]; [name]; [name], [name])  | Version Number: | Final 8.0 |

Version Date: 06MAR2018

Template No: CS\_TP\_BS016 – Revision 2  
 Effective Date: 01Feb2010

Reference: CS\_WI\_BS005

Statistical Analysis Plan

---

**7.4.2. Demographic and Other Baseline Characteristics**

The following demographic and baseline characteristics will be summarized for the ITT population.

Demography: Gender, age (calculated from date of birth and date of screening visit), height, weight (at screening), BMI (at screening), ECOG PS (at screening) and race.

Primary Diagnosis: Body Site, time since date of histopathological diagnosis (calculated as number of years from date of histopathological diagnosis to date of screening visit), histological classification, risk group.

Medical History: Medical history will be coded using the latest version of Medical Dictionary for Regulatory Activities (MedDRA) and summarized by system organ class (SOC) and preferred term (PT).

Prior Medication/Therapy: Prior medications, as defined in Section 7.5.5, will be summarized by the Anatomical Therapeutic Chemical (ATC) Classification System and WHO Drug name. Prior non-drug treatments, as defined in Section 7.5.5, will be provided in a listing.

Signs and Symptoms: Signs and symptoms are defined as any events recorded in the medical history page ongoing at screening. They will be summarized by SOC and PT.

**7.4.3. Extent of Exposure**

Study treatment exposure will be summarized for all subjects in the as-treated population. The number of subjects who completed at least 3 years of study medication, at least 2 years of study medication and at least 1 year of study medication will be provided. Duration of exposure to study medication will be calculated as the number of months from date of first dose to date of last dose + 1 day. For the purposes of categorization of exposure duration, the following conversions (assuming a -14 day window) will be used:

- 1-351 days = “0 - <12 months”
- 352-716 days = “12 - <24 months”
- 717-1081 days = “24 - <36 months”
- >1081 days = “≥36 months”.

Reasons for treatment withdrawal will be provided.

Overall duration of exposure to study medication will be summarized by treatment group using summary statistics.

Also, the total dose prescribed in milligrams (mg) and the actual dose administered will be summarized.

Number and percentage of subjects with dose increases, dose reductions and dose interruptions

---

|           |   |                 |           |
|-----------|---|-----------------|-----------|
| Document: | C:\Users\q764206\AppData\Local\Microsoft\Windows\Temporary Internet Files\Content.Outlook\GWW33WM3\ATLAS_SAPFinal v8.0_06MAR2018.docx |                 |           |
| Author:   | [name] (Updated [name]; [name]; [name], [name])  | Version Number: | Final 8.0 |
|           |   | Version Date:   | 06MAR2018 |

Template No: CS\_TP\_BS016 – Revision 2  
 Effective Date: 01Feb2010

Reference: CS\_WI\_BS005

Statistical Analysis Plan

---

will be summarized.

Other summaries will include:

- Descriptive statistics for time to the first actual dose interruption, dose reduction and dose increase
- Descriptive statistics for time to the second actual dose interruption, dose reduction and dose increase
- Descriptive statistics for time to the third actual dose interruption, dose reduction and dose increase
- Descriptive statistics for time to first dose interruption, time to first dose interruption that was  $\geq 7$  days,  $\geq 14$  days, and  $\geq 21$  days after first dose date. The time to dose interruption is calculated as (start date of the interruption – first dose date + 1).
- Descriptive statistics for time to second dose interruption, time to second dose interruption that was  $\geq 7$  days,  $\geq 14$  days, and  $\geq 21$  days after first dose date.
- Relative dose: percent of actual total dose received relative to intended total dose initially planned per protocol (5mg BID), where actual total dose= total dose received as recorded on CRF, and intended total dose = (prescribed dose at beginning of the study) $\times$ (actual dose duration).

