#### 6.5.1. Withdrawal from treatment

Patients will be withdrawn from treatment in the case of:

- Recurrence or occurrence of a secondary malignancy. Investigators are encouraged
  to await the result of the IRC assessment before making treatment decisions unless
  clinical considerations require immediate intervention eg, in the case of brain
  metastases;
- Unacceptable toxicity;
- Need for anticancer therapy not specified in the protocol;
- Congestive heart failure;
- Repeated noncompliance;
- Patient becomes pregnant;
- Patient lost to follow-up;
- Patient choice to withdraw from treatment (follow-up permitted by patient)

If patients require >2 consecutive weeks of dose interruption, a discussion should be made in consultation with the medical monitor.

Data to be collected for the end of study treatment/withdrawal from treatment are described in the End of Study Treatment/Withdrawal from treatment Procedures section (Section 6.2.3). Patients will be followed up for at least 28 days after the last dose of study drug for adverse events and concomitant medications and treatments

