**6.1.1. Analyses for Continuous Data**

For continuous data, the following summary statistics will be presented: n, mean, standard deviation (StD), median, minimum and maximum.

Mean and median values will be reported to one decimal place greater than the original data they were collected from while the StD will be reported to two decimal places greater than the original data. Minimum and maximum values will be reported with the same precision as they were collected.

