**6.1.3. Analysis of Time-To-Event Endpoints**

Time-to-event endpoints will be summarized using the Kaplan-Meier method and displayed graphically when appropriate. Median event times and 2-sided 95% CI for each median will be provided based on the Brookmeyer-Crowley method.

Difference in time-to-event endpoints will be tested using a 2-sided stratified or unstratified log-rank test, where applicable. The stratified analysis will be performed as stated in Section 5.4.1.

Cox proportional hazards model will be used to estimate the hazard ratio and its 95% CI.

A parametric model will also be implemented as a sensitivity analysis of DFS.

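### SAP 7.4.3 words its 7, 14 and 21-day interruption limits as days since first dose, and its 'time to' dose-change summaries take no account of time on treatment

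*SAP*

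**What the plan says.** SAP 7.4.3 (Extent of Exposure) lists several dose-change summaries for the as-treated population.

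- One bullet asks for "Descriptive statistics for time to the first actual dose interruption, dose reduction and dose increase". Matching bullets cover the second and third occurrence.
- A further bullet asks for "Descriptive statistics for time to first dose interruption, time to first dose interruption that was" ≥7, ≥14 and ≥21 "days after first dose date. The time to dose interruption is calculated as (start date of the interruption" minus first dose date plus 1).
- The same construction is repeated: "Descriptive statistics for time to second dose interruption, time to second dose interruption that was" ≥7, ≥14 and ≥21 days after first dose.

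The section also gives the number and percentage of subjects with increases, reductions and interruptions, the duration of exposure, the reasons for treatment withdrawal, and relative dose. None of the listed summaries reports how long an interruption lasted.

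SAP 6.1.1 defines the descriptive statistics: "For continuous data, the following summary statistics will be presented: n, mean, standard deviation (StD), median, minimum and maximum". No censoring is involved. Protocol 6.5.1 treats length as the quantity that triggers action: "If patients require >2 consecutive weeks of dose interruption, a discussion should be made in consultation with the medical monitor".

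**The concern.** There are two separate issues.

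First, the sentence places the day limits next to the first dose date, and the only derivation given uses the start date of the interruption. A programmer following the words would select on how late the interruption began. The result would be three further rows that mostly repeat a number already tabulated, and nothing on prolonged interruptions of a drug given for up to 3 years. A second programmer could reasonably read the limits as length and produce a quite different table.

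Second, a mean or median time to a dose change among those who had one depends on how long subjects stayed on treatment as well as on the risk of the change. Treatment ends at recurrence, secondary malignancy, toxicity or withdrawal, so time at risk can differ by arm. An arm that leaves treatment sooner will show shorter times even if its risk is the same, because late events are never observed.

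**Working it through.** The plan states no figure for interruption timing, so there is none to reproduce.

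**1. The two readings, by example.** A subject has a first interruption starting on day 30 and lasting 2 days, and a second starting on day 90 and lasting 16 days. On the literal reading the ≥14-day value is 30. On the length reading it is 90.

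**2. How far the literal rows repeat the plain row.** Assume a constant interruption hazard λ, a treatment-stop hazard μ, r = λ + μ, and the 3-year cap from the protocol. Among interrupted subjects, the share whose first interruption starts at least L after first dose is

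[exp(−rL) − exp(−3r)] / [1 − exp(−3r)].

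With λ = 0.5 and μ = 0.25 per year (assumed), r = 0.75 and exp(−2.25) = 0.1054:
- L = 7 days: (0.9857 − 0.1054)/0.8946 = 98.4%
- L = 14 days: (0.9717 − 0.1054)/0.8946 = 96.8%
- L = 21 days: (0.9578 − 0.1054)/0.8946 = 95.3%

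A simulation of 200,000 subjects per arm took recurrence from the SAP's 2-year DFS rates and 90/1/9% risk mix. It assumed 30, 50 or 70% interrupted by 1 year and other discontinuation of 0-40% per year. The shares were about 96-99%, 93-98% and 90-96%. In one axitinib scenario (50% interrupted by 1 year, 20% discontinuing per year) the medians for the plain, ≥7, ≥14 and ≥21-day rows were 226, 233, 240 and 247 days.

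The share depends on when interruptions occur. At λ = 2 and μ = 0.60, r = 2.6 and the 21-day share is (0.8612 − 0.0004)/0.9996 = 86%. Now suppose instead a six-fold hazard in the first 6 weeks, base 0.5 per year, stopping 0.35 per year:
- event before day 21: (3/3.35)(1 − exp(−3.35 × 21/365.25)) = 0.157
- event by day 42: (3/3.35)(1 − exp(−3.35 × 42/365.25)) = 0.286
- event after day 42: 0.6803 × (0.5/0.85)(1 − exp(−0.85 × 2.885)) = 0.366
- share unchanged at 21 days: 1 − 0.157/(0.286 + 0.366) = 76%

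With a base of 2 per year the share is about 48%.

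**3. What the length reading gives.** In the axitinib scenario above (50% by 1 year, 20% discontinuation), with mean interruption length assumed to be 10 days, 45.6%, 27.7% and 15.2% of subjects have an interruption lasting ≥7, ≥14 and ≥21 days. The median time to one lasting ≥21 days is 372 days, against 247 in the literal row.

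**4. Times among subjects with the event.** Under constant hazards the median is

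m = −ln{1 − ½[1 − exp(−3r)]}/r.

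With the interruption hazard equal in both arms:

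| λ per year | μ per year, two arms | r | Median, days | Difference |
|---|---|---|---|---|
| 0.5 | 0.25 vs 0.60 | 0.75 vs 1.10 | 289 vs 218 | 71 |
| 0.5 | 0.30 vs 0.40 | 0.80 vs 0.90 | 277 vs 255 | 22 |
| 2.0 | 0.25 vs 0.60 | 2.25 vs 2.60 | 112 vs 97 | 15 |

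Simulating the first row gave 290 vs 217 days, a difference of 73.

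Simulated medians (days, axitinib vs placebo) with recurrence from the SAP's DFS assumptions and equal interruption risk. The last column gives both arms the same exposure:

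| Interrupted by 1 year | Exposure differs through DFS only | Other discontinuation 20% vs 5%/yr | 40% vs 5%/yr | Equal exposure |
|---|---|---|---|---|
| 30% | 361 vs 341 | 297 vs 327 | 236 vs 323 | 300 vs 297 |
| 50% | 270 vs 255 | 226 vs 246 | 184 vs 246 | 228 vs 226 |
| 70% | 186 vs 176 | 159 vs 170 | 136 vs 171 | 161 vs 160 |

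The 12-month Kaplan-Meier probability of a first interruption, censored at end of treatment, agreed between arms within 0.4 percentage points in every scenario.

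**The case against.** The strongest reply is that this is a wording query. The sentence can be parsed as the time, counted from first dose, to the first interruption that was ≥7 days long. The formula defines only the time, so it would omit length on either reading. The SAP's contents list table shells, which are not in the text reviewed and might settle the matter. This stands: a reader might infer that the SAP deliberately chose the start-time rule, and the text does not establish that. What remains is that the literal words point one way, the likely intent points the other, and they appear twice.

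A reader might also infer that the plan contradicts SAP 6.1.3, which says "Time-to-event endpoints will be summarized using the Kaplan-Meier method and displayed graphically when appropriate". It does not. Dose-change times are not among the endpoints named in SAP section 5. They sit under extent of exposure, where descriptive statistics are requested explicitly.

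The times are purely descriptive, SAP 7.5 plans no formal safety comparison, and incidence and exposure duration appear in the same section. That limits the harm. It does not make the conditional medians comparable between arms, and SAP 7.5.1.2 already plans Kaplan-Meier displays for time to first adverse event of special interest.

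**Conclusion.** The point holds as a minor one. As worded, the 7, 14 and 21-day limits attach to days since first dose, with length the likely but unstated intent. On the literal reading the rows are near-copies, not exact copies, of the first-interruption time. The 90-99% figure assumes a constant hazard with 30-70% interrupted by 1 year; it falls to 86% at 2 interruptions per year with stopping at 0.60 per year, and to 76-48% under the early-clustering assumption.

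That the 'time to' summaries cover only subjects with the event is inferred from the request for descriptive statistics; the SAP does not say so. A reader might infer that the arms will differ whenever risk is equal. The documents do not support that: the difference needs unequal time on treatment, and with equal exposure it vanishes (228 vs 226 days). Nor is the 73-day result an estimate for this trial; it is one scenario. Across the simulated scenarios the axitinib median ran from 20 days longer to 87 days shorter than placebo. Size and direction depend on discontinuation rates the documents do not give.

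DFS, OS, event counts, alpha and adverse-event incidence are untouched. Only descriptive exposure tables are affected.

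**What to change.** In SAP 7.4.3:

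- Define interruption length as stop date − start date + 1.
- Replace the two limit bullets with: *time from first dose to the start of the first (second) dose interruption lasting ≥7, ≥14 and ≥21 consecutive days*. This also removes a smaller ambiguity: with the + 1 in the formula, an interruption starting 7 days after first dose has time 8, and the SAP does not say which scale the limit uses.
- Add a Kaplan-Meier summary of time to first interruption, first reduction and first increase in all as-treated subjects, censored at last dose, with the percentage having the event at fixed times (for example 3, 6, 12 and 24 months) by arm. Note that censoring at last dose describes risk while on treatment and assumes stopping is unrelated to that risk. The number and percentage of subjects with each event, already planned, should stay beside it.

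The cost is a few lines of SAP text, matching table-shell edits and slightly longer tables. Interruption stop dates are needed as well as the start dates the formula already uses.

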**7.5. Analysis of Safety**

All safety analyses will be performed using the As-Treated population. No formal comparisons between the two treatment arms are planned. Safety and tolerability will be assessed by the incidence of treatment emergent-adverse events (TEAEs), changes in laboratory parameters and vital signs from baseline, and ECG.

An independent DMC will monitor safety during the study on a regular basis. The committee will operate independently from the Sponsor and the clinical investigators.

The primary responsibility of the DMC is to review the accumulating safety data on a regular and an ad hoc basis and make recommendations to the Sponsor regarding the continued conduct of the study. Safety data will be provided at regular intervals to the DMC in the form of summary reports or data listings from the Sponsor or its designated representative.

Details regarding DMC membership, schedule and format of meetings, format for presentation of data, access to interim data, method and timing of providing interim reports to the DMC, and

---

|           |   |                 |           |
|-----------|---|-----------------|-----------|
| Document: | C:\Users\q764206\AppData\Local\Microsoft\Windows\Temporary Internet Files\Content.Outlook\GWW33WM3\ATLAS_SAPFinal v8.0_06MAR2018.docx |                 |           |
| Author:   | [name] (Updated [name]; [name]; [name], [name])  | Version Number: | Final 8.0 |
|           |   | Version Date:   |           |

06MAR2018

Template No: CS\_TP\_BS016 – Revision 2  
 Effective Date: 01Feb2010

Reference: CS\_WI\_BS005

**Statistical Analysis Plan**

---

other issues relevant to committee operations are described in the DMC charter.

The DMC members will use their expertise, experience, and judgment to evaluate the safety data from the trial and to recommend to the Sponsor whether the trial should continue or be stopped early for safety.

**7.5.1. Adverse Events**

Adverse event (AE) terms recorded on the CRF will be mapped to PT and SOC using the Medical Dictionary for Regulatory Activities (MedDRA). The severity of AEs will be evaluated by the investigator by employing the CTCAE v4.03 (Cancer Terminology Criteria for Adverse Events). The investigator will also judge each event to be “not related” or “related” to study treatment.

A TEAE is defined as any AE with an onset date on or after the date of the first dose of study treatment or any ongoing event on the date of the first dose of study treatment that worsens in severity after the date of the first dose of study treatment.

The AE observation period is defined as the time from date of the first dose of study treatment until 28 days after the last dose of study drug is administered. TEAEs with an onset date through the end of the study observation period will be summarized by treatment arms. The Grade 5 TEAEs with onset date outside of the observation period may be tabulated separately.

For summaries of subject incidence of TEAE, at each level of summarization, a subject will be counted only once for each AE preferred term experienced by the subject within that level (i.e., multiple episodes of events with the same preferred terms will be counted only once). Selected summaries of subject-incidence of AEs (as defined in Section 7.5.1.2) will include the risk difference (defined as the proportion with the event in the axitinib arm minus the proportion with the event in the placebo treatment arm) with 95% CIs and the risk ratio (or relative risk; defined as the proportion with the event in the axitinib group divided by the proportion with the event in the placebo group) with 95% CIs. An overall summary of treatment emergent adverse events (including those that stopped more than 28 days after the decision to discontinue study treatment) will be provided with the number and percent of subjects who experienced the following in each treatment group:

- Subjects with a TEAE
- Subjects with a Related TEAE
- Subjects with a Serious TEAE at any time (including active treatment period plus follow-up period)
- Subjects with a Serious Related TEAE
- Subjects with a Worst-Grade of  $\geq 3$  TEAE
- Subjects with a Worst-Grade of  $\geq 3$  Related TEAE
- Subjects with a Grade 5 TEAE at any time

---

|           |   |                 |           |
|-----------|---|-----------------|-----------|
| Document: | C:\Users\q764206\AppData\Local\Microsoft\Windows\Temporary Internet Files\Content.Outlook\GWW33WM3\ATLAS_SAPFinal v8.0_06MAR2018.docx |                 |           |
| Author:   | [name] (Updated [name]; [name]; [name], [name])  | Version Number: | Final 8.0 |
|           |   | Version Date:   | 06MAR2018 |

Template No: CS\_TP\_BS016 – Revision 2  
 Effective Date: 01Feb2010

Reference: CS\_WI\_BS005

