Several anti-angiogenic agents have shown activity in the treatment of mRCC. In the first-line treatment of mRCC, sunitinib has demonstrated dramatically improved median progression free survival (PFS) over IFN (11 months vs 5 months; hazard ratio 0.42; p < 0.001) and is now considered to be the standard of care for the first-line treatment of patients with mRCC. In similar first-line setting, the final analysis of a randomized Phase 3 (AVOREN) trial of bevacizumab in combination with IFN versus IFN alone demonstrated that bevacizumab significantly improved PFS and showed a trend toward improvement in OS in patients with mRCC.  In second-line setting after cytokine failure, sorafenib has demonstrated superior PFS over placebo with the median PFS of 5.5 months.

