## 5.3.4.2. Axitinib/Placebo Dose Reduction for Hypertension

Patients treated with axitinib/placebo will be issued blood pressure cuffs (provided by Sponsor) for home monitoring and instructed to measure their blood pressure prior to taking each dose of study drug (twice daily) for the first 3 months, and once a week thereafter. Following dose modification of study drug or anti-hypertensive medication, or changes of anti-hypertensive medication, patients must restart blood pressure measurements prior to taking each dose of study drug for the first 3 months and once a week thereafter. All BP measurements will be recorded in a diary by the patient themselves and brought to the nurse or study coordinator at each clinic visit. Patients should be instructed by the study staff to contact their investigator immediately for guidance if their sBP rises above 150 mm Hg, or dBP rises above 100 mm Hg, or if they develop symptoms perceived to be related to elevated BP (eg, headache, visual disturbance). See below for dose modifications for hypertension.

New or additional antihypertensive therapy (See Section 5.5.1, Concomitant Medication) should be started if 2 BP readings, taken at site and separated by at least 5 minutes in the seated position after the patient has been sitting quietly for 5 minutes, show the following: 2 sBP readings >150 mm Hg or 2 dBP readings >100 mm Hg. Alternately, the dose of existing antihypertensive medication(s) may be increased. If the patient is already on maximal antihypertensive treatment, the axitinib/placebo dose should be reduced by 1 dose level.

Patients who have 2 sBP readings, separated by at least 5 minutes, greater than 160 mm Hg, or 2 dBP readings, separated by at least 5 minutes in the seated position after the patient has been sitting quietly for 5 minutes, greater than 105 mm Hg, will have treatment with axitinib/placebo interrupted. (Note: if axitinib/placebo is interrupted, patients receiving antihypertensive medications should monitor closely for hypotension and restart axitinib/placebo at one lower dose level as soon as BP is ≤150/100 mm Hg. Plasma half-life of axitinib is 2-4 hours and BP usually decreases within 1-2 days following dose interruption.) Treatment with axitinib/placebo should be restarted at 1 lower dose level as soon as the sBP reduces to less than or equal to 150 mm Hg and the dBP reduces to less than or equal to 100 mm Hg.

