## 8.2. Reporting Period

Serious adverse events require immediate notification to sponsor or its designated representative beginning from the time that the patient provides informed consent, which is obtained prior to the patient's participation in the clinical trial, ie, prior to undergoing any trial-related procedure and/or receiving investigational product, through and including 28 calendar days after the last administration of the investigational product. Any serious adverse event occurring any time after the reporting period must be promptly reported if a causal relationship to investigational product is suspected.

Non-serious adverse events should be recorded from the time the patient has taken at least one dose of trial treatment through last patient visit.

If a patient begins a new anticancer therapy, the adverse event reporting period for non-serious adverse events ends at the time the new treatment is started. Death must be reported if it occurs during the serious adverse event reporting period after the last dose of investigational product, irrespective of any intervening treatment.

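### The all-causality adverse event tables do not separate events that begin after a new anti-tumor therapy, and the protocol's rules for collecting non-serious events after that switch disagree; the effect is probably small

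*SAP*

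**What the plan says.** **Analysis window.** SAP 7.5.1 states: "The AE observation period is defined as the time from date of the first dose of study treatment until 28 days after the last dose". Its definition of a treatment-emergent event (TEAE) has a start but no end: "A TEAE is defined as any AE with an onset date on or after the date of the first dose of study treatment". Protocol 9.4.1 treats all events, serious and non-serious, up to 28 days after treatment as treatment-emergent. Neither document mentions a new anti-tumor therapy here.

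**Lines without a time limit.** The SAP 7.5.1 overview includes "Subjects with a Serious TEAE at any time (including active treatment period plus follow-up period", and an all-causality Grade 5 line that is also unlimited in time.

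**Between-arm measures.** SAP 7.5.1 plans risk differences and risk ratios with 95% confidence intervals for the special-interest categories of SAP 7.5.1.2. These are not restricted to related events.

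**Collection.** Under Protocol 8.2, when a patient begins a new anticancer therapy, "the adverse event reporting period for non-serious adverse events ends at the time the new treatment is started". Serious events are reportable "through and including 28 calendar days after the last administration of the investigational product", and deaths in that period "irrespective of any intervening treatment". Footnote 18 of the Schedule of Assessments and Protocol 6.3 and 6.5.1 collect adverse events to 28 days after the last dose with no stop at new therapy.

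**The concern.** Study drug stops at recurrence, or when another anticancer therapy is needed (Protocol 6.5.1). A patient who starts that therapy within 28 days of the last dose remains inside the SAP window. A serious or severe event on the new drug is then tabulated under the study arm.

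The next drug may share axitinib's toxicities. Protocol 1.1.1 discusses sunitinib among the anti-angiogenic agents and says it "is now considered to be the standard of care for the first-line treatment of patients with mRCC". Hypertension, haemorrhage, proteinuria and palmar-plantar erythrodysesthesia are among the special-interest categories. If axitinib works, placebo has more recurrences and so probably more early switches. Next-drug events would then raise placebo counts somewhat more and slightly understate the axitinib excess.

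The planned outputs would not show this readily. SAP 7.5.5 counts anti-tumor drugs as follow-up treatment only if they start more than 28 days after the last study treatment, so that table omits the patients concerned.

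**Working it through.** **1. The rules after a switch inside the 28 days**

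| Source | Non-serious events | Serious events and deaths |
|---|---|---|
| Protocol 8.2 | stop at new therapy | continue to day 28 |
| Schedule footnote 18; Protocol 6.3, 6.5.1 | continue to day 28 | continue to day 28 |
| Protocol 9.4.1 | counted to day 28 | counted to day 28 |
| SAP 7.5.1, main tables | counted to day 28 | counted to day 28 |
| SAP 7.5.1, serious line and one all-causality Grade 5 line | n/a | counted without limit |

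Serious events after a switch are collected and counted under every rule. Whether non-serious events are collected depends on which section a site follows. After day 28, Protocol 8.2 asks for a serious event only if study-drug causality is suspected, which limits next-drug events in the unlimited lines.

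**2. The plan's own figure** (Protocol 9.1)

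Hazard ratio = ln(2-year DFS on axitinib) / ln(2-year DFS on placebo):

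- category 1: ln 0.79 / ln 0.70 = 0.661
- category 2: ln 0.61 / ln 0.35 = 0.471
- category 3: ln 0.51 / ln 0.33 = 0.607
- weighted: 0.90 × 0.661 + 0.01 × 0.471 + 0.09 × 0.607 = 0.654, as stated.

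**3. DFS events by arm under the design** (350 per arm, exponential)

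- *Within 1 year, the stated minimum treatment duration, no drop-out:* 350 × Σ share × (1 − √(2-year DFS)).
  - Placebo: 350 × (0.90 × 0.163 + 0.01 × 0.408 + 0.09 × 0.425) = 66.3.
  - Axitinib: 350 × (0.90 × 0.111 + 0.01 × 0.219 + 0.09 × 0.286) = 44.8.
  - Ratio 1.48.
- *Within 3 years, the maximum treatment duration, no drop-out:* 158.8 against 115.7, ratio 1.37.
- *At 245 events in total,* with uniform accrual over 24 months and a drop-out hazard of −ln(0.77)/1.5 = 0.174 per year: 141.3 against 103.7, ratio 1.36.

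These counts are upper bounds on switching inside the window. DFS events include deaths, and recurrences long after the last dose.

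**4. Subjects with a post-switch serious event in the window**

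Neither rate needed is in the documents. Assume 30-70% of patients with a DFS event start new therapy within 28 days of the last dose, and 2-6% of those have a serious event in the rest of the window. The multiplier runs from 0.3 × 0.02 = 0.006 to 0.7 × 0.06 = 0.042.

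| Base | Placebo | Axitinib | Net placebo excess |
|---|---|---|---|
| 1-year events (66.3 / 44.8) | 0.4 to 2.8 | 0.3 to 1.9 | 0.1 to 0.9 |
| At 245 events (141.3 / 103.7) | 0.8 to 5.9 | 0.6 to 4.4 | 0.2 to 1.6 |

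The largest net figure is 1.6 of 350, about 0.5 percentage points.

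*Sensitivity.* With 10-50% switching and 5-20% having a serious event, the multiplier is 0.005 to 0.10. On the 3-year counts without drop-out the net is 43.1 × 0.005 = 0.2 to 43.1 × 0.10 = 4.3 subjects, up to 1.2 percentage points. The size is driven by the assumptions.

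**The case against.** The strongest reply is that the SAP follows the protocol. Protocol 9.4.1 defines TEAEs to day 28, and Protocol 8.2 expressly keeps deaths whatever treatment intervenes. All-causality counting to day 28 is a recognisable conservative choice, and no formal safety comparison is planned (SAP 7.5). Related-only rows are planned and anti-tumor therapy is recorded, so post-switch cases can be identified. All of this stands. The related rows are only a partial answer, because the special-interest risk differences are not restricted to related events and Protocol 8.8 handles unknown causality as related for reporting.

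Three stronger readings are tempting, and the documents do not support them:

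- *After a switch the tables hold only serious events.* That follows only if Protocol 8.2 overrides footnote 18 and sections 6.3 and 6.5.1. What can be said is that capture is uneven.
- *The 28-day window is what places post-switch events in the serious count.* That line has no time limit, so shortening the window alone would not remove them.
- *Placebo toxicity will be materially inflated.* The sunitinib statement concerns metastatic disease and says nothing about switching within 28 days. Investigators are also encouraged to await independent review before treatment decisions (Protocol 6.5.1), which may delay a switch.

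Nor does the statement "Plasma half-life of axitinib is 2-4 hours" show that little would be lost by closing the window at the switch. The protocol ties it to blood pressure, and it does not settle how long thyroid, thromboembolic or renal effects last.

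**Conclusion.** The point holds as an inexpensive improvement. The main all-causality summaries take no account of new anti-tumor therapy, two overview lines have no time limit, and the protocol disagrees with itself on non-serious collection after a switch. Grade 3 or higher, serious and special-interest counts can therefore include next-drug events.

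The placebo-heavy direction is conditional on axitinib working as designed and on similar switching behaviour in both arms. The net excess is about 0.1 to 1.6 subjects in total under the main assumed rates, and up to about 4.3 under the wider ones. Under the main rates, with the special-interest list running to more than a dozen categories, the net effect would usually be below one subject in any one category. A reader might infer a distorted safety comparison, but nothing in the documents supports an effect of that size.

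**What to change.** 1. In SAP 7.5.1, end the main all-causality TEAE summaries, including the special-interest risk differences and ratios, at the earlier of 28 days after last dose and the day before the first new anti-tumor therapy. Align Protocol 9.4.1.
2. Flag every adverse event with onset on or after that therapy. Tabulate post-switch serious events, Grade 5 events and deaths in a separate row by arm.
3. Split the serious and Grade 5 lines that have no time limit into before and after new therapy.
4. Reconcile Protocol 8.2 with footnote 18 and sections 6.3, 6.5.1 and 9.4.1, so that one rule governs non-serious collection after a switch.

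**Cost.** SAP wording, a short protocol clarification and one date comparison. The start date of anti-tumor therapy already drives DFS censoring in SAP Appendix A, Table 1.

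**Downside.** Delayed study-drug events after an early switch move to the separate row, and the main window is shortened more often in the arm with more recurrences. The separate row keeps those serious events and deaths visible.
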